22.5 Patient information at trial unblinding

Upon trial unblinding each trial participant will be informed about the administered treatment.

23 ADMINISTRATIVE CONSIDERATIONS

23.1 Insurance

The SAKK will indemnify patients for damages they have suffered as participants in the trial. For this purpose, SAKK has taken out a special insurance for clinical trials with Chubb Insurance Company of Europe SE, [name], Switzerland.

23.2 Monitoring and auditing

All source data must be accessible for auditing and monitoring. CRAs and auditors will maintain patient confidentiality.

23.2.1 Monitoring strategy

This trial will be monitored. The SAKK is performing risk-adapted monitoring according to the concept developed by the ADAMON group. Based on the risk analysis, low monitoring strategy has been chosen. The different monitoring activities as well as the frequency of the visits are described in a trial-specific monitoring plan.

23.2.2 Auditing/inspecting

Authorities have the right to perform inspections, and the SAKK has the right to perform on-site auditing during working hours upon reasonable prior notice.

23.3 Quality control and quality assurance

Several procedures ensure the quality of the trial in compliance with applicable regulatory requirements, GCP and the protocol:

- Written standard operating procedures are implemented
- Personnel involved in conducting the trial is qualified by education, training and experience
- An updated staff list must be kept at the site
- Validation of database and statistical analysis
- Quality control principles are implemented (randomization and blinding procedures require double signatures and are documented)
- On-site and central monitoring evaluates protocol compliance (SDV, verification of informed consent etc.) by personnel designated by the SAKK
- Data captured online is validated in real-time, yielding errors (for unacceptable data) and warnings (for possibly inconsistent data - these warnings may be overruled by the user)
- Audit trail of changes
- Medical data review is performed by the coordinating investigator or a delegated person (all CRFs will be reviewed and checked on medical content)
- Central management of deviations and implementation of corrective and preventive measures
- Independent data monitoring committee
- Central PIK3CA mutation screening
- Safety monitoring
- Accountability of IMP (aspirin or placebo) and patient diary
- Internal audit procedures

23.4 Trial activation procedure

The procedure for trial activation at a site is described in the final protocol letter, which is sent to the investigators who committed to participate in the trial. All participating investigators must follow the instructions given in this letter for the preparation of site documents.

Upon receipt of the site documents, the SAKK CC - or the Cooperative Group or appointed CRO in EU (in agreement with the specificities defined in the contract with foreign sites and the Cooperative Group/appointed CRO) - will proceed with the submission to the relevant ECs and competent authorities.

Any site which is interested to participate in the trial but has not committed yet, is requested to contact the SAKK CC. The SAKK CC will evaluate the feasibility of the site participation and initiate the trial activation steps for the site if applicable.

The investigator is only allowed to screen and register patients into the trial after the involved ECs, Swissmedic or the responsible competent authorities in EU countries authorized the trial at the site and the SAKK CC opened the site for accrual.

23.5 Local trial records

23.5.1 Investigator's file

All trial-related correspondence should be filed in the investigator's file. A suggested table of contents (according to ICH E6, chapter 8) is provided on the SAKK portal (portal.sakk.ch → Trials → SAKK 41/13-Aspirin → useful tools).

23.5.2 Useful tools

CRFs, drug order forms and accountability logs, documents required for EC approval, a schedule of assessments etc. can be downloaded from the SAKK portal (portal.sakk.ch → Trials → SAKK 41/13-Aspirin).

23.5.3 Record retention

The site will retain all essential documents according to ICH/GCP. This includes copies of the patient trial records, which are considered as source data, patient informed consent statement, laboratory printouts, drug inventory and destruction logs, and all other information collected during the trial. These documents will be stored for at least 10 years in Switzerland (at least 15 years in EU countries) after the termination of the trial. The start and the end of this retention period will be communicated to the sites by the SAKK CC.

For the patient trial records, which are entered into the EDC system, the sponsor guarantees the access and availability of the data at any time for at least 10 years (respectively, 15 years in EU) after the termination of the trial. The data of patients who consented to the banking of their clinical data and their biological material may be used for additional investigations in the field of cancer. The banking of data must conform to the HRA and its corresponding ordinances, and to the recommendations from the Swiss Ethics Committees on research involving humans. The SAKK will be the exclusive owner of any data, discoveries, or derivative materials from the banked data. The patient will have no commercial rights to the data, information, discoveries, or derivative materials gained or produced from the banked data.

The patient retains the right to have their recorded clinical data irreversibly anonymized at any time by contacting the principal investigator according to the HRA and its applicable ordinances. The SAKK will be responsible for the anonymization of the data at the request of the patient. However, data which is already obtained from this material can be used for the intended analysis.

In the event that the principal investigator retires or changes employment, custody of the records may be transferred to another competent person who will accept responsibility for those records. Written notice of such transfer will be given to the SAKK CC. The SAKK will notify the concerned regulatory authorities.

23.6 Trial registration

The SAKK will register the trial at www.clinicaltrials.gov and on the SNCTP at www.kofam.ch. With the participation of sites in the EU it will also be registered with the EudraCT database (<https://eudract.emea.europa.eu>) of clinical trials.

23.7 Participation of local and foreign sites

A list of sites and investigators that have agreed to participate in the trial are given in a separate document which can be downloaded from portal.sakk.ch (→ Trials → SAKK 41/13-Aspirin).

Separate trial-specific agreements will be issued for participating sites outside of Switzerland.

23.8 Modifications of the protocol

23.8.1 Substantial amendment

Any amendment which may have an impact on the conduct of the trial, the potential benefit of the trial, or may affect patient safety, including changes of trial objectives, trial design, patient population, sample sizes, trial procedures, or significant administrative aspects. Such an amendment must be accepted by the SAKK Board and must have the authorization of the respective EC and competent authority (if applicable) prior to implementation.

23.8.2 Safety amendment

A safety amendment is a special kind of substantial amendment which is released when it is necessary to eliminate immediate hazards to trial participants. A safety amendment requires immediate implementation at local sites and is submitted in parallel for authorization to the ECs and the competent authority (if applicable).

23.8.3 Non substantial amendment

Non-substantial amendments such as minor corrections and/or clarifications that have no effect on the way the trial is conducted have to be submitted to the ECs once a year, together with the submission of the annual DSUR. Non-substantial amendments which affect the evaluation of the competent authority have to be submitted to the CA as soon as possible.

23.9 Trial termination

The SAKK CC is responsible for submitting the information about trial termination to the national authorities according to local legislation (e.g. Switzerland, according to HRA).

24 PUBLICATION

The results of the trial will be published according to the current version of the SAKK publication guidelines (available on the SAKK portal). The SAKK publication guideline guarantees the freedom of reporting of the participating physicians.

25.2 Confidentiality

Trial-related data of the patient will be provided in a coded manner to the SAKK CC. The names of the patients will not be disclosed to the SAKK CC. A unique patient number (UPN) will be attributed to each patient registered into the trial.

Identification of patients must be guaranteed at the site. For this purpose, sites are requested to use the patient screening and enrollment and the patient identification lists specifically produced for the trial (available on the SAKK portal). In order to avoid identification errors, the year of birth and the UPN have to be provided on the CRFs. Patient confidentiality will be maintained according to the locally applicable legislation. Patients must be informed of, and agree to, data and material transfer and handling, in accordance with the Swiss data protection law.

All information concerning the IMP supplied by Bayer in connection with this trial and not previously published is considered confidential and proprietary information.

27 APPENDICES

Appendix 1 TNM Classification

According to UICC 2009 [64].

T - Primary tumor

- TX Primary tumor cannot be assessed
- T0 No evidence of primary tumor
- Tis Carcinoma in situ: intraepithelial or invasion of lamina propria
- T1 Tumor invades submucosa
- T2 Tumor invades muscularis propria
- T3 Tumor invades through the muscularis propria into the pericolorectal tissues
- T4a Tumor penetrates to the surface of the visceral peritoneum
- T4b Tumor directly invades or is adherent to other organs or structures

N - Regional lymph nodes

- NX Regional lymph nodes cannot be assessed
- N0 No regional lymph node metastasis
- N1 Metastasis in 1-3 regional lymph nodes
- N1a Metastasis in 1 regional lymph node
- N1b Metastasis in 2-3 regional lymph nodes
- N1c Tumor deposit(s) in the subserosa, mesentery, or nonperitonealized pericolic or perirectal tissues without regional nodal metastasis
- N2 Metastasis in 4 or more lymph nodes
- N2a Metastasis in 4-6 regional lymph nodes
- N2b Metastasis in 7 or more regional lymph nodes

M - Distant metastasis

- M0 No distant metastasis
- M1 Distant metastasis
- M1a Metastasis confined to 1 organ or site (e.g., liver, lung, ovary, non-regional node)
- M1b Metastases in more than 1 organ/site or the peritoneum

Stage	T	N	M
0	Tis	N0	M0
I	T1, T2	N0	M0
II	T3, T4	N0	M0
IIA	T3	N0	M0
IIB	T4a	N0	M0
IIC	T4b	N0	M0
III	Any T	N1, N2	M0
IIIA	T1, T2	N1	M0
	T1	N2a	M0
IIIB	T3-T4a	N1	M0
	T2-T3	N2a	M0
	T1-T2	N2b	M0
IIIC	T4a	N2a	M0
	T3, T4a	N2b	M0
	T4b	N1, N2	M0
IVA	Any T	Any N	M1a

IVB	Any T	Any N	M1b
-----	-------	-------	-----

Histopathological Grading

GX: The tumor grade cannot be identified.

G1: The cells look more like normal tissue cells (well differentiated).

G2: The cells are somewhat different (moderately differentiated).

G3: The cells look very unlike normal cells (poorly differentiated).

G4: The cells barely resemble normal cells (undifferentiated).

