4.1 Methods of minimizing bias

4.1.1 Randomization and stratification

Patients are randomized in a 2:1 ratio to the aspirin or placebo arm using the minimization method with 80% allocation probability according to the stratification factors:

- Stage II versus stage III colon cancer
- Left versus right hemicolon
- PIK3CA mutation in exon 9 versus 20
- Country

A total of 185 patients (123 in the aspirin arm and 62 in the placebo group) were planned to be randomized.

Due to the premature closure for accrual of the trial, 113 patients were randomized.

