15 STATISTICAL CONSIDERATIONS

15.1 Sample size estimation

- Software package: East 6.2
- Number of treatment arms: 2
- Type of design: parallel design
- Trial intention: superiority
- Statistical test: One-sided log-rank test
- Null hypothesis: hazard ratio (HR) 1.0
- Alternative hypothesis: HR 0.456 (corresponding to a 3-year DFS of 70% in the placebo arm and 85% in the aspirin arm assuming constant hazards). This hazard ratio is based on the two published retrospective studies: The hazard ratio for cancer-specific survival in the study by Liao et al. [13] was 0.18, the hazard ratio in the study by Domingo et al. [14] for recurrence was 0.11. Therefore, the assumed hazard ratio of 0.456 in this trial represents a conservative estimate. The assumption of a 3-year DFS of 70% in the placebo arm was based on several studies [4, 13, 14, 26] as well as analyses of the SEER data base (<http://seer.cancer.gov/data/>) and analyses performed on data of the Cantonal Hospital St. Gallen.
- Type I error: 5%
- Power: 80%
- Randomization ratio: 2:1
- Number of interim analyses for the primary endpoint: Two
- Timing of interim analyses: after 25% (11) and 50% (22) of the events, the first is expected after approximately 2.4 years of accrual and the second after approximately 0.5 years of follow-up.
- Stopping boundary for benefit/futility: Lan-DeMets error spending function in spirit of the O'Brien & Fleming boundary [27, 28].
- Expected accrual rate: 60 patients per year
- Expected accrual time: 3 years
- Expected follow-up time until primary analysis: 3 years
- Expected proportion of lost to follow-up: 20%. This is based on various studies assessing aspirin intake [29-31].
- Required number of events: 43
- Sample size: 185 (123 in the aspirin group, 62 in placebo group)

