- Number needed to screen: 1850 assuming 17% PIK3CA mutations in colorectal cancer patients; estimate of 17% is based on New England Journal of Medicine publication [13]. PIK3CA mutations in colorectal cancer patients are described between 15% and 20% in the literature. The rate of PIK3CA mutation is relatively lower in rectal cancer (approximately 8%, [22]) compared to colon cancer. Therefore, by excluding rectal cancer patients, the estimate of a PIK3CA mutation rate of 17% is conservative. However, as not all the mutated patients will be included in the trial due to patient's wish, ineligibility discovered after PIK3CA screening, etc., it is assumed that 10% of all screened patients will be finally randomized in the trial.

Note: These calculations are based on the formula for the log-rank test. Due to the asymptotic equivalence of the test statistic of the Cox regression model without covariates and the log-rank test statistics under the assumed model, the sample size calculation holds also true for the unadjusted Cox regression model. It can be expected that inclusion of the stratification factors in the analysis will further increase the power as compared to the above calculations that are based on the Cox regression model without covariates.

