15.3 Statistical analyses

The primary analysis will take place once the 43rd DFS event has taken place or at the latest after 3 years from the date of surgery of the last included patient.

All efficacy endpoints will be analyzed based on the full analysis population. Supportive analyses based on the PP population will be performed. All safety endpoints will be analyzed based on the safety population. Subgroup analyses for all stratification factors except country are planned for the primary endpoint. All time-to-event endpoints shall have the median value of each treatment group estimated using the Kaplan-Meier method, along with a 95% confidence interval. The number of events of each endpoint shall be presented descriptively by frequency and percentage by treatment arm. The treatment effect will be assessed using Cox regression models with the treatment arm as independent variable and the stratification factors as strata. Cox regression models will also be used to investigate the potential effects of other factors (e.g. chemotherapy given and concomitant therapy) on selected endpoints. Subgroup analyses may be performed for these factors. For the primary analysis, patients who were unblinded before experiencing an event will be censored at the date of the last available tumor assessment before unblinding. A supportive analysis will be performed in which the unblinding will not be considered.

Categorical variables will be summarized with frequency and percentage and may be compared between arms by chi-square tests or Fisher's exact tests. Continuous variables will be summarized using median and range and may be compared between arms by t-tests or Wilcoxon rank sum tests.

Laboratory values will be expressed as the absolute values and as grading according to NCI CTCAE v4.0 by treatment arm. AE grading shall be presented by type, grade, and relation showing frequency and percentage of the within-patient worst grades by treatment arms. In addition, grade ≥ 3 AEs and AEs with relation to treatment ≥ 3 will be summarized separately.

Full analysis details will be outlined in the statistical analysis plan (SAP).

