17.1 Local pathology

17.1.1 Task of the local investigator

The local investigator at each participating site is responsible to inform the local pathologist about the protocol, the trial-specific investigations and the sample handling for central PIK3CA mutation testing and translational research/sample banking.

It is the task of the local investigator to determine the disease stage according to the TNM classification (7th edition, October 2009, see Appendix 1) and to order tumor blocks at the local pathology. **The investigator must ensure that informed consent for PIK3CA mutation analysis was obtained from the patient before ordering the pathology sample.**

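### The primary DFS model is valid but carries tumour stage only as II versus III; one pre-specified T/N covariate would correct chance imbalance within stage, for a small gain in power

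*Combined protocol and SAP*

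**What the plan says.** Section 15.3 estimates the treatment effect on the time-to-event endpoints with "Cox regression models with the treatment arm as independent variable and the stratification factors as strata"; the statistical part of the trial overview says the same. Section 4.1.1 lists four factors: "Stage II versus stage III colon cancer", left or right hemicolon, PIK3CA exon 9 or 20, and country. No finer T or N category enters the model.

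The finer information is generated. Under 17.1.1, "It is the task of the local investigator to determine the disease stage according to the TNM classification", and 17.1.2 requires the local pathologist to apply the same TNM edition. Appendix 1 splits the eligible stages into IIA-IIC and IIIA-IIIC, with entries such as "N2 Metastasis in 4 or more lymph nodes". Section 2.2 lists T4 among the high-risk features of stage II disease.

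The sample-size note in 15.1 expects that "inclusion of the stratification factors in the analysis will further increase the power". Section 15.3 also allows Cox models for other factors, with chemotherapy and concomitant therapy as examples, but these do not define the treatment-effect model. It defers full details to a SAP whose text is not in the supplied document.

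**The concern.** pT and pN come from the resection specimen, so treatment cannot affect them. If they carry prognostic information within stage, leaving them out of a Cox model has two effects. The hazard ratio is pulled slightly towards 1, with some loss of power. And since the minimisation balances stage II versus III but not T4 or N2 within stage, a chance difference between arms goes uncorrected into the DFS estimate. The second effect matters more after early closure: 113 patients were randomised instead of 185 (section 4.1.1), so chance differences are larger. The reasoning is the one that 15.1 already applies to the stratification factors.

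**Working it through.** **1. The plan's own figure.** Inputs from 15.1: "Statistical test: One-sided log-rank test", type I error 5%, power 80%, HR 0.456, "Randomization ratio: 2:1".

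- HR: ln 0.85 / ln 0.70 = 0.1625 / 0.3567 = 0.456.
- Aspirin share of events under the alternative: p = 2×0.456 / (1 + 2×0.456) = 0.477.
- Events: [1.645/√(2/9) + 0.842/√(0.477×0.523)]² / (ln 0.456)² = (3.489 + 1.685)² / 0.617 = 43.4, against 43 stated.

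The stated figure reproduces and does not depend on T or N.

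**2. Size of a chance imbalance.** The documents give no T4 or N2 prevalence and no final arm sizes. Assumed: 75 and 38 patients (113 at 2:1), 60% stage III, 20% pT4, and 35% of stage III pN2. High risk means pT4 or pN2.

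- High-risk share: stage II 0.20; stage III 0.20 + 0.80×0.35 = 0.48.
- Variance with stage balanced: 0.4×0.20×0.80 + 0.6×0.48×0.52 = 0.214.
- SD of the arm difference: √[0.214×(1/75 + 1/38)] = √(0.214×0.0396) = 0.092, or 9.2 points.
- pT4 alone (20%): √(0.16×0.0396) = 0.080, or 8.0 points.

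For a generic 30% risk group, the SD is √[0.21×(1/75 + 1/38)] = 9.1 points, and a difference above 10 points has probability about 27%. At the planned 123 and 62 patients these become 7.1 points and about 16%.

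**3. Effect on the hazard ratio.** To first order the log HR shifts by imbalance × ln(prognostic HR).

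| Imbalance (pT4 or pN2) | Prognostic HR 2 | Prognostic HR 2.5 |
|---|---|---|
| 1 SD (0.092) | exp(0.064) = 1.07 | exp(0.084) = 1.09 |
| 2 SD (0.184) | exp(0.128) = 1.14 | exp(0.169) = 1.18 |

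At 2 SD, a true 0.456 would read as about 0.52-0.54, or as about 0.39-0.40 in the other direction. For pT4 alone the multipliers are 1.06-1.08 at 1 SD (exp(0.055), exp(0.073)) and 1.12-1.16 at 2 SD (exp(0.110), exp(0.146)).

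Simulation agrees: each 10 points of imbalance moved the log HR by about 0.04, 0.07 and 0.12 for prognostic HRs of 1.5, 2 and 3. With the covariate in the model the movement fell to about 0.02 or less.

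**4. Power.** Simulated with minimisation at 80% probability on the four factors and 1600 runs per scenario. Assumed: 30% high-risk within stage, 60% stage III with HR 2, four countries, true HR 0.456. The 26 events are pro rata: 43×113/185 = 26. Cells show power (%) without → with the covariate.

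| Prognostic HR | 43 events; strata stage, side, exon | 43 events; plus country | 26 events; strata stage, side, exon | 26 events; plus country |
|---|---|---|---|---|
| 1.5 | 79.9 → 80.3 | 72.4 → 72.3 | 59.9 → 60.3 | 48.6 → 49.9 |
| 2 | 78.0 → 79.1 | 72.0 → 73.4 | 59.2 → 60.1 | 48.6 → 49.2 |
| 3 | 76.1 → 79.9 | 70.4 → 72.0 | 55.9 → 59.7 | 47.1 → 49.6 |

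Each figure has a simulation standard error of about 1.0-1.3 points (√(0.8×0.2/1600) to √(0.25/1600)). A separate simulation at about 18 events found no clear change: 41.3 → 40.1 with all four strata and 52.5 → 54.2 with stage only.

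**5. Validity and attenuation.** With no treatment effect and prognostic HRs of 1.5 to 3, rejection rates at 43 events were 5.4-6.7% without the covariate and 5.4-6.6% with it. At 26 events they were 4.5-5.2% and 4.9-5.5%. For a true 0.456 at 43 events (strata stage, side, exon), the median HR was 0.456, 0.461 and 0.470 without the covariate, and 0.452, 0.452 and 0.454 with it.

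**The case against.** The plan contains no error on this point. No stated figure is wrong, and chance imbalance is not bias: the confidence interval already allows for it. With 2:1 allocation and 18 events, SE(log HR) = 1/√(18×2/9) = 0.50, so even the 2-SD shift of 0.13-0.17 is about a quarter to a third of one standard error. Events may well be few. The planned rates give 75×0.15 + 38×0.30 = about 23 at three years before losses, and 15.3 censors at unblinding, which reached every site in December 2020 (section 7.5). All of this stands and limits the benefit.

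A reader might infer more than the documents support:

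- **That T/N is shown to be a strong predictor.** Section 2.2 names T4 without an effect size, and nothing is said on the prognosis of N2 against N1; the Appendix 1 line is only a classification entry. The one contrast that 2.2 quantifies, recurrence of up to 25% in stage II and up to 50% in stage III, is already a stratum.
- **That nothing else of possible prognostic value is in the model.** Side, exon and country are strata too.
- **That sub-staging is an eligibility requirement.** Sections 6.1.3 and 12.1 ask only for stage II or III; the TNM requirement sits in 17.1.
- **That the factors 15.3 gives as examples all arise after randomisation.** Section 9.5 lets chemotherapy start before trial entry.

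The coding is also open to challenge. A pT4-or-pN2 indicator marks T1 N2a (IIIA) as high risk and T3 N1 (IIIB) as low risk. Other markers have a claim as well: differentiation and invasion in 2.2, HLA class I in 18.1.3, BRAF and MSI in 18.1.4. Finally, the separate SAP may already contain such a model. These arguments favour a single modest covariate, preferably the supported component, but do not remove the gap in 15.3.

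**Conclusion.** The point holds as an inexpensive improvement in precision, not as the correction of a fault. The DFS model is valid as written. It leaves unused a baseline classification that 17.1 requires, one component of which (T4) the protocol itself calls high risk, and so it does not correct chance imbalance within stage.

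The main benefit is protection of the estimate: with 113 patients, about 7-9% on the hazard ratio for a 1-SD imbalance and 14-18% for 2 SD. The power gain is about 0 to 4 points, with none clear near 18 events. These sizes rest on assumed prevalences, arm sizes and prognostic hazard ratios (2 to 2.5 for the shift, 1.5 to 3 for power), because the documents supply none. To read this as an invalid or biased primary test would be wrong: the simulated type I error is about the same with and without the covariate.

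**What to change.** In section 15.3 and the SAP, pre-specify one binary baseline covariate for high-risk pathology in the primary DFS Cox model, beside treatment arm and the existing strata. pT4 is the component that the documents support; pT4 or pN2 is the wider alternative. Enter it as a covariate, not as a further stratum: the plan already has eight stage-by-side-by-exon cells multiplied by country. In the simulation, stratifying by country (four assumed) cost 6-8 points of power at 43 events, more than this adjustment recovers. Report the model without the covariate alongside.

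Two steps come first. Confirm that pT and pN are eCRF fields or can be taken from the pathology reports required in 17.1.3; the baseline items in 7.4 and 12.1.2 do not name them. And check that the separate SAP does not already specify this. Because sites know their patients' allocation, record the choice, dated, as made before outcome data are examined by arm.

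The cost is a sentence of text, one degree of freedom, possible retrieval of T and N from reports, and a hazard ratio that is conditional on the covariate. Little power is gained if events stay low.
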